8.2 Subject demographics/other baseline characteristics

Patient information to be collected at screening include:

- a. Demography
- b. Complete Medical History and current medical conditions
- c. Prior and concomitant medications and non-therapies (including physical therapy, oxygen and blood transfusions)
- d. Disease History – disease treatment history, donor background, stem cell transplant and GvHD disease history including CIBMTR classification ([Section 16.5](#) Appendix 5) and HCT specific comorbidity index score ([Section 16.4](#) Appendix 4)

Patient will have the screening assessments performed before the start of study treatment as in [Table 8-1](#):

- Physical examination including height, weight, vital signs
- Laboratory assessments – Hematology, Chemistry, Coagulation, Urinalysis
- Hepatitis serology markers
- Pregnancy test (for applicable female patients only, [Section 8.5.5](#))
- Graft failure assessment

- aGvHD disease staging ([Table 8-2](#)) ([Harris et al 2016](#)) Biopsy confirmation of aGvHD is recommended but is not required. Enrollment should not be delayed awaiting biopsy or pathology results.
- Graft failure baseline assessment

■

The investigator must confirm all the inclusion and exclusion criteria prior to contacting IRT for dose assignment. Once the patient's eligibility is confirmed, the patient must have baseline assessments performed on Day 1 prior to treatment initiation ([Table 8-1](#)).

Please refer to sections below for related assessments.

8.3 Treatment Period

Study treatment will be initiated on Day 1 of dose assignment by IRT system.

- Day 1 is defined as the first day of treatment initiation.
- After Day1 visit will occur at the following frequency as specified in [Table 8-1](#).
 1. Every week until Week 8 (+/- 3 days)
 2. Every 4 weeks until Week 24 (+/- 7 days) or the end of treatment EOT visit
 3. Every 4 weeks until Week 48 (+/-7 days) – for patients with taper or aGvHD flare ([Section 6.1.5.1.1](#)) or the end of treatment EOT visit

Study treatment will be administered until aGvHD progression, graft failure, hematologic disease progression, occurrence of AE, or patient discontinuation [Section 9.1](#)

End of treatment visit will occur upon discontinuation of study treatment. This may be at Week 24, Week 48 (in case of taper/aGvHD flare) or earlier.

Unscheduled visits may be performed as necessary. Additional assessments may be done as per institutional guidelines at investigator's discretion at any time during the trial. aGvHD assessments performed at unscheduled visit and leading to a change in patient's management or, during treatment period to a change in patient's response should be recorded in the CRF, as well as any relevant safety assessment performed.

8.4 Efficacy

8.4.1 Staging and Response assessments

8.4.1.1 aGvHD staging

Organ staging of aGvHD will be performed according to updated NIH criteria as described by [Harris et al 2016](#) in the table below.

■

Table 8-2 Acute GvHD Staging Criteria (Harris et al 2016)

Stage	Skin (Active Erythema Only)	Liver (Bilirubin)	Upper GI	Lower GI (stool output/day)
Stage 0	No active (erythematous) GVHD rash	< 2mg/dL	No or intermittent nausea, vomiting, or anorexia	Adult: <500mL/day or < 3 episodes/day Child: <10mL/kg/day or < 4 episodes/day
Stage 1	Maculopapular rash < 25% BSA	2 – 3 mg/dL	Persistent nausea, vomiting, or anorexia	Adult: 500-999 mL/day or 3-4 episodes/day Child: 10-19.9 mL/kg/day or 4-6 episodes/day
Stage 2	Maculopapular rash < 25-50% BSA	3.1 – 6 mg/dL		Adult: 1000-1500mL/day or 5-7 episodes/day Child: 20-30mL/kg/day or 7-10 episodes/day
Stage 3	Maculopapular rash > 50% BSA	6.1 – 15 mg/dL		Adult: >1500mL/day or > 7 episodes/day Child: >30mL/kg/day or > 10 episodes/day
Stage 4	Generalized erythroderma (>50% BSA) plus bullous formation and desquamation > 5% BSA	> 15 mg/dL		Severe abdominal pain with or without ileus or grossly bloody stool (regardless of stool volume)

Overall clinical grade (based on most severe target organ involvement):

Grade 0: No stage 1-4 of any organ.

Grade I: Stage 1-2 skin without liver, upper GI or lower GI involvement.

Grade II: Stage 3 rash and/or stage 1 liver and/or stage 1 upper GI and/or stage 1 lower GI.

Grade III: Stage 2-3 liver and/or stage 2-3 lower GI with stage 0-3 skin and/or stage 0-1 upper GI.

Grade IV: Stage 4 skin, liver or lower GI involvement, with stage 0-1 upper GI.

8.4.1.2 aGvHD assessment

aGvHD grading will be performed by the investigator on a weekly basis for the first 8 weeks after treatment assignment and then every 28 days thereafter during the treatment period and at EOT visit as outlined in [Table 8-1](#).

aGvHD assessment will be performed as per [Table 8-2 \(Harris et al 2016\)](#): organ assessment (skin; liver; upper GI; Lower GI) and overall grading at the time of the evaluation should be reported according to [Table 8-2](#).

In addition, biopsy of the organ involved may be performed per institutional practices at investigator's discretion for aGvHD management. If performed, the investigator will indicate the results once available.

Response to study treatment will be assessed by the investigator at every visit during the treatment period ([Section 8.3](#)). Response assessment by the investigator at Day 28 and at Day 56 will support respectively, the primary and key secondary endpoint assessments for this trial.

Patients will be also monitored for aGvHD flares occurring during steroid, CNI, and ruxolitinib taper.

Investigator should carefully record any action taken to manage aGvHD including start of tapering, initiation of any new systemic therapy, re-escalation of corticosteroids and the re-escalated steroid dose, and steroid taper failure.

The data should be entered in the appropriate CRFs. Worsening of aGvHD, including occurrence of GvHD flare will be reported on appropriate specific CRF and, not as an adverse event ([Section 10.1.1](#)).

Note: Additional assessments may be done as per institutional guidelines at investigator's discretion. aGvHD assessments performed at unscheduled visit and leading to a change in patient's management or a change in patient's response should be recorded in the CRF.

Table 8-3 Response assessment

Efficacy assessments:

aGvHD response assessment will be made with respect to the organ stage at screening and Day 1:

4. **Complete response** is defined as a score of 0 for the aGvHD grading in all evaluable organs that indicates complete resolution of all signs and symptoms of aGvHD in all evaluable organs without administration of additional systemic therapy for any earlier progression, mixed response or non-response of aGvHD.
5. **Partial response** is defined as improvement of 1 stage in 1 or more organs involved with aGvHD signs or symptoms without progression in other organs or sites without administration of additional systemic therapy for an earlier progression, mixed response or non-response of aGvHD.
6. **Lack of response** is defined as no response, mixed response, or progression.
7. **No response** is defined as absence of improvement in any organ involved by aGvHD, without worsening in any involved organ.
8. **Mixed response** is defined as improvement of at least 1 stage in the severity of aGvHD in one organ accompanied by progression in another organ or development of signs or symptoms of aGvHD in a new organ.
9. **Progression** is defined as worsening in 1 or more organs by 1 or more stages without improvement in any involved organ.

Patients requiring additional systemic therapy for aGvHD will be classified as non-responders.

aGvHD Flare is defined as any increase in signs or symptoms of aGvHD that is sustained for >24h after an initial response (CR or PR) and requires re-escalation of immunosuppressive therapy (e.g. corticosteroid, CNI and/or ruxolitinib dosing). While all aGvHD flares will be captured on study whether occurring during steroid, CNI, or ruxolitinib taper, only flares that fulfill either one the following criteria will be considered a failure of treatment:

1. Addition of new systemic therapy for aGvHD due to inability to taper corticosteroids below methylprednisolone 0.5 mg/kg/day (or equivalent <0.6 mg/kg/day of prednisone) for a minimum 7 days,
OR
2. Addition of new systemic therapy for aGvHD due to re-escalation of corticosteroids to methylprednisolone >2 mg/kg/day (or equivalent >2.5 mg/kg/day of prednisone).

aGvHD assessments will be performed by the treating team according to standard criteria ([Harris et al 2016](#)) as described in [Table 8-3](#). Disease assessments must continue per the schedule of visits weekly until Day 56, unless withdrawal of consent/ Opposition to use data/biological samples or death occurs, even in patients who are withdrawn from treatment unless consent for these assessments is specifically withdrawn.

At later time points after Day 56 after the start of the study treatment, signs and symptoms of cGvHD may be observed. cGvHD signs and symptoms may occur in up to 50% of patients based on published literature. Patients will be evaluated for any signs or symptoms of cGvHD and scored using NIH Consensus Criteria (Lee et al 2015) as described in [Section 16.2](#) (Appendix 2). Development of cGvHD signs or symptoms is not considered a treatment failure of aGvHD. Treatment of cGvHD will follow institutional standards of procedure and Investigator preference. Ruxolitinib must not be administered for treatment of cGvHD. For patients receiving ruxolitinib at the time of onset of cGvHD, ruxolitinib taper will follow guidelines per [Section 6.1.5.1](#).

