7. Phase II To measure the activity of ruxolitinib in patients with aGvHD or SR-aGvHD assessed by Overall Response Rate (ORR) at Day 28.	8. Overall response rate (ORR) at Day 28, defined as the proportion of patients demonstrating a complete response (CR) or partial response (PR) without requirement for additional systemic therapies for an earlier progression, mixed response or non-response. Scoring of response will be relative to the organ stage at the start of the study treatment.
Secondary objective(s)	Endpoint(s) for secondary objective(s)
9. Key Secondary To assess the rate of durable ORR at Day 56	10. Proportion of all patients who achieve a CR or PR at Day 28 and maintain a CR or PR at Day 56
11. To estimate ORR at Day 14	12. Proportion of patients who achieved OR (CR+PR) at Day 14
13. To assess pharmacokinetic/pharmacodynamic relationships	14. PK parameters (such as AUC, Cmax, Ctrough) versus safety, efficacy, and PD biomarkers, as appropriate
15. To assess Duration of response	16. Duration of response (DOR) is assessed for responders only and is defined as the time from first response until aGvHD progression or the date of additional systemic therapies for aGvHD. Onset of chronic GvHD, or death without prior observation of aGvHD progression are considered as competing risks
17. To assess the cumulative steroid dose until Day 56	18. Weekly cumulative steroid dose for each patient up to Day 56

Objective(s)	Endpoint(s)
19. To evaluate the safety and tolerability of ruxolitinib	20. Safety and tolerability including myelosuppression, infections, and bleeding will be assessed by monitoring the frequency, duration and severity of Adverse Events including occurrence of any second primary malignancies, infections, by performing physical exams, and evaluating changes in vital signs from baseline, routine serum chemistry, hematology results and coagulation profile
21. To assess Overall Survival (OS)	22. Overall survival, defined as the time from the start of treatment to the date of death due to any cause
23. To assess Event-Free Survival (EFS)	24. Event-free survival, defined as the time from start of treatment to the date of hematologic disease relapse/progression, graft failure, or death due to any cause
25. To assess Failure-Free Survival (FFS)	26. Failure-free survival, defined as the time from the start of treatment to date of hematologic disease relapse/progression, non-relapse mortality, or addition of new systemic aGvHD treatment

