8.1 Screening

Molecular pre-screening

Not Applicable

Screening

Patients diagnosed with either aGvHD (grades II-IV) or SR-aGvHD (grades II-IV) after alloSCT will be consented to the study prior to any study procedures being performed.

Screening period will begin once the patient has signed the Study Informed Consent and will be a maximum of 28 days (Day -28 to Day -1).

Screening procedures are outlined in the visit evaluation schedule ([Table 8-1](#)) including blood samples tested as needed, and assessment of inclusion and exclusion criteria.

All study procedures should be performed within 28 days before treatment initiation on Day 1. Laboratory assessments should be performed within 72 hours of treatment initiation. Continued use of systemic corticosteroids, CNI (cyclosporine or tacrolimus), and topical corticosteroid therapy per institutional guidelines is permitted. Other systemic medications for aGvHD may be continued after Day 1 only if used for aGvHD prophylaxis prior to diagnosis of aGvHD. For SR-aGvHD patients, cessation of other systemic treatment for aGvHD other than corticosteroids +/- CNI will be required prior to treatment initiation.

A patient who has a laboratory test result(s) that does not satisfy the entrance criteria may have the test(s) repeated. These tests may be repeated as soon as the investigator believes the retest result is likely to be within the acceptable range to satisfy the entrance criteria, and can be completed within the 28 day screening period. In this case, the patient will not be required to sign another ICF, and the original patient ID number assigned by the investigator will be used.

All baseline assessments should be performed on Day 1 as per [Table 8-1](#). Laboratory assessments performed within 72 hours of Day 1 need not be repeated.

A patient is considered a screen failure in the event that the laboratory test(s) cannot be available within the screening period, or the retest(s) do not meet the entrance criteria or the patient's medical condition has changed significantly during the screening period so that the inclusion/exclusion criteria are no longer met, more details outlined on [Section 5](#).

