12.4.1 Definition of primary endpoint(s)

The primary endpoint of the Phase I is the list of following PK parameters (AUC, Cmax, T1/2, Ctrough, and other parameters, as appropriate) which will be derived using non-compartmental methods in subjects with extensive sampling (Groups 1, 2, and 3). These parameters will then be used to define a RP2D for Groups 2, 3, and 4. The observed PK parameters (within group) will be summarized and compared to information obtained from adult and adolescent aGvHD patients treated with ruxolitinib on study [\[CINC424C2301\]](#). Data from patients older than 2 years old will be combined and analyzed by PBPK methods to determine the dose to be administered in patients younger than 2 years old (Group 4).

The primary endpoint for the Phase II is the overall response rate (ORR) at Day 28, defined as the proportion of patients with complete response (CR) or partial response (PR) without requirement for additional systemic therapies for an earlier progression, mixed response or non-response as per [Table 8-3 \(Harris et al 2016\)](#). Note that response is relative to the assessment of aGvHD at the start of study treatment.

- **Complete-response** is defined as a score of 0 for the aGvHD grading in all evaluable organs that indicates complete resolution of all signs and symptoms of aGvHD in all evaluable organs without administration of additional systemic therapies for any earlier progression, mixed response or non-response of aGvHD.
- **Partial response** is defined as improvement of 1 stage in 1 or more organs involved with aGvHD signs or symptoms without progression in other organs or sites without administration of additional systemic therapies for an earlier progression, mixed response or non-response of aGvHD.
- **Lack of response** is defined as no response, mixed response, or progression.
- **No response** is defined as absence of improvement in any organ involved by aGvHD, without worsening in any involved organ.
- **Mixed response** is defined as improvement of at least 1 stage in the severity of aGvHD in at least one organ accompanied by progression in another organ or development of signs or symptoms of aGvHD in a new organ.
- **Progression** is defined as worsening in 1 or more organs by 1 or more stages without improvement in any involved organ

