Patients requiring additional systemic therapy for aGvHD will be classified as non-responders, and patients with missing baseline or Day 28 aGvHD response assessment will be considered as treatment non-responders.

aGvHD Flare is defined as any increase in signs or symptoms of aGvHD that is sustained for >24h after an initial response (CR or PR) and requires re-escalation of immunosuppressive therapy (e.g. corticosteroid, CNI and/or ruxolitinib dosing). While all aGvHD flares will be captured on study whether occurring during steroid, CNI or ruxolitinib taper. Only flares in GvHD that require new additional systemic therapy, will be considered aGvHD flare failure.

Acute GvHD will be assessed as per [Table 8-2 \(Harris et al 2016\)](#). Grade will be calculated based on the staging of the organs and recorded on the eCRF by the Investigator. The Investigator reported grade will be used for all analyses. Grade and response will be calculated by the sponsor for the purposes of data review and sensitivity analysis.

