12.4.3 Handling of missing values/censoring/discontinuations

Patients with missing assessments that prevent the evaluation of the ORR will be considered non-responders. This includes aGvHD response assessments at baseline and Days 28, 56. Patients who discontinue the study treatment prior to the completion of the Day 28 visit will be considered non-responders.

The following analysis windows will be applied to the target day for assessments on overall response, where target day for Week X is X*7.

Baseline assessment is the last aGvHD assessment prior to or at the start of study treatment (Day 1).

Weeks 1, 2, 3, 4, 5, 6, 7, 8: -3 days/+3 days

Weeks 12 to 48: -13 days/+14 days

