3.5.1 Primary endpoint

The primary endpoint of the Phase I is the list of following PK parameters (AUC, Cmax, T1/2, Ctrough, and other parameters, as appropriate) which will be derived using non-compartmental methods in subjects with extensive sampling (Groups 1, 2, and 3). These parameters will then be used to define a RP2D for Groups 2, 3, and 4. The observed PK parameters (within group) will be summarized and compared to information obtained from adult and adolescent aGvHD patients treated with ruxolitinib on study CINC424C2301. Data from patients older than 2 years old will be combined and analyzed by PBPK methods to determine the dose to be administered in patients younger than 2 years old (Group 4).

The primary endpoint for the Phase II is the investigator-reported overall response rate (ORR) at Day 28, defined as the proportion of patients with complete response (CR) or partial response (PR) without requirement for additional systemic therapies for an earlier progression, mixed response or non-response as per [Table 8-3](#) of the protocol ([Harris et al 2016](#)). Note that response is relative to the assessment of aGvHD at the start of study treatment.

- **Complete-response** is defined as a score of 0 for the aGvHD grading in all evaluable organs that indicates complete resolution of all signs and symptoms of aGvHD in all evaluable organs without administration of additional systemic therapies for any earlier progression, mixed response or non-response of aGvHD.
- **Partial response** is defined as improvement of 1 stage in 1 or more organs involved with aGvHD signs or symptoms without progression in other organs or sites without administration of additional systemic therapies for an earlier progression, mixed response or non-response of aGvHD.
- **Lack of response** is defined as no response, mixed response, or progression.
- **No response** is defined as absence of improvement in any organ involved by aGvHD, without worsening in any involved organ.
- **Mixed response** is defined as improvement of at least 1 stage in the severity of aGvHD in at least one organ accompanied by progression in another organ or development of signs or symptoms of aGvHD in a new organ.
- **Progression** is defined as worsening in 1 or more organs by 1 or more stages without improvement in any involved organ

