Patients requiring additional systemic therapy for aGvHD will be classified as non-responders, and patients with missing baseline or Day 28 aGvHD response assessment will be considered as treatment non-responders.

aGvHD Flare is defined as any increase in signs or symptoms of aGvHD that is sustained for >24h after an initial response (CR or PR) and requires re-escalation of immunosuppressive therapy (e.g. corticosteroid, CNI and/or ruxolitinib dosing). While all aGvHD flares will be captured on study whether occurring during steroid, CNI or ruxolitinib taper. Only flares in GvHD that require new additional systemic therapy, will be considered aGvHD flare failure.

Acute GvHD will be assessed as per [Table 8-2](#) of the protocol. Grade will be calculated based on the staging of the organs and recorded on the eCRF by the Investigator. The Investigator reported grade will be used for all analyses. Grade and response will be calculated by the sponsor for the purposes of data review.

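### Table 8-3 gives investigators two reference stagings for response (screening and Day 1), the endpoint definition uses one, and no rule says which governs when they differ

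*Protocol*

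**What the plan says.** Table 8-3 (protocol 8.4.1.2) opens the response definitions with: "aGvHD response assessment will be made with respect to the organ stage at screening and Day 1". Section 8.4.1.2 makes this table the treating team's instrument, and both protocol 12.4.1 and SAP 3.5.1 cite it for the response criteria.

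Elsewhere there is a single reference. Table 2-1 has: "Scoring of response will be relative to the organ stage at the start of the study treatment". The protocol summary agrees. Protocol 12.4.1 has: "Note that response is relative to the assessment of aGvHD at the start of study treatment", and SAP 3.5.1 repeats it. Protocol 12.4.3, mirrored in SAP 3.5.3, has: "Baseline assessment is the last aGvHD assessment prior to or at the start of study treatment (Day 1)".

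Table 8-1 schedules acute GvHD staging at screening and again on Day 1. On the gap between them, protocol 8.1 has: "All study procedures should be performed within 28 days before treatment initiation on Day 1".

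On whose call is analysed, SAP 3.5.1 has: "The primary endpoint for the Phase II is the investigator-reported overall response rate (ORR) at Day 28". On the sponsor's own derivation the two documents differ. Protocol 12.4.1: "Grade and response will be calculated by the sponsor for the purposes of data review and sensitivity analysis". SAP 3.5.1 stops earlier: "Grade and response will be calculated by the sponsor for the purposes of data review". SAP section 5 nevertheless records no change from the protocol.

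**The concern.** Partial response needs only one stage of improvement in one organ, so the choice of reference staging can decide it. Stage can move between screening and Day 1. Steroid-refractory patients are on systemic steroids at entry (protocol 5.1), and treatment-naïve patients may have had up to 72 hours of them (protocol 5.2).

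An investigator who follows Table 8-3 literally has two references and no tie-break. Two sites can score the same course differently. A change that took place before the first ruxolitinib dose can then count for or against the drug in an endpoint meant to measure its activity. Day 14 response, durable response at Day 56, best overall response and duration of response use the same scoring.

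The SAP's baseline rule does not cure this, because the analysed value is the investigator's reported response. The planned sensitivity analysis in SAP 3.5.4 does not cure it either. It removes patients whose staging or response assessment departed from the protocol's criteria, and scoring against screening follows Table 8-3, so it need not be logged as a deviation.

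**Working it through.** **1. Does the reference change the call?** Take lower GI involvement only, with other organs at stage 0 throughout. Under Table 8-2, lower GI stage 1 is Grade II and stage 2 is Grade III, so both courses stay within the Grade II-IV entry criterion at both pre-dose stagings.

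| Lower GI stage: screening / Day 1 / Day 28 | Against Day 1 | Against screening | Improvement required on both |
|---|---|---|---|
| 2 / 1 / 1 | No response | PR | Not a PR |
| 1 / 2 / 1 | PR | No response | Not a PR |

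The three readings of the Table 8-3 lead-in give different answers, and the difference runs both ways. CR is unaffected, since it requires stage 0 in all evaluable organs whichever reference is used.

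**2. Reproduce the plan's figure.** Inputs from protocol 12.8.1 and Table 12-2: n = 45, assumed true ORR 80%, two-sided 90% Clopper-Pearson interval, marker of a lower limit of at least 60%.

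- Lower limit for x responders = 5th percentile of Beta(x, n − x + 1). Upper limit = 95th percentile of Beta(x + 1, n − x).
- The smallest x with a lower limit of at least 0.60 is 33, with interval 0.604 to 0.838. Table 12-2 gives the same.
- P(X ≥ 33 | n = 45, p = 0.80) = 0.9005, against 0.901 in the table. Reproduced.

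**3. Effect of net reclassification.** One patient is 1/45 = 2.2 percentage points. The planned result is 0.80 × 45 = 36 responders.

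| Responders of 45 | Net change from 36 | 90% lower limit |
|---|---|---|
| 38 | +2 | 0.728 |
| 37 | +1 | 0.702 |
| 36 | 0 | 0.677 |
| 35 | −1 | 0.652 |
| 34 | −2 | 0.628 |
| 33 | −3 | 0.604 |
| 32 | −4 | 0.580 |

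From 36 responders, four net reclassifications are needed to fall below 0.60. From exactly 33, one is enough. The net changes are assumed values: the documents do not report how many patients changed stage before dosing, nor how many of those would change responder status.

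**The case against.** The strongest reply is that the endpoint text settles the matter. Directly after citing Table 8-3, protocol 12.4.1 and SAP 3.5.1 add that response is relative to the start of treatment, and the baseline rule names one assessment. Table 8-3 may simply be listing the two scheduled pre-dose stagings. This shows what was intended, but it does not re-score a call already made by an investigator using Table 8-3.

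The gap between stagings may also be short. Inclusion criterion 3 requires Grade II-IV disease to be clinically confirmed within 48 hours before treatment, and protocol 5.1 places consent at the time of diagnosis. The 28-day window is therefore an upper bound that many patients will not approach. That stands and limits the likely number affected. It does not date the screening staging or say which staging governs.

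Sponsor review is a natural route for catching discordant calls. That also stands, but the SAP attaches no query rule and no analysis to it.

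A reader might infer that the wording inflates ORR. The documents do not support a direction: worsening before Day 1, which is plausible in steroid-refractory disease, makes a screening reference harder to meet, and requiring improvement on both is stricter still.

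A reader might also infer that patients who cleared before Day 1 would be credited as CR because of this wording. CR is the same under either reference, so that does not follow.

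**Conclusion.** The inconsistency is in the current text and reaches the primary endpoint. It can misplace patients between PR and no response, mixed response or progression at Day 28 and in the related response endpoints. Its size and direction cannot be estimated from the documents.

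It would be too strong to say that a single patient decides the study. That holds only at exactly 33 responders; from the planned 36, four net reclassifications in the same direction are needed. The 60% limit is also a planning marker for precision, since protocol 12.7 and SAP 3.14 test no efficacy hypothesis.

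The conclusion rests on two points: at least some investigators may have scored against screening, as Table 8-3 allows, and some patients' organ stages differed between the two visits. Neither can be confirmed or excluded from the plan. Without the protocol's sensitivity analysis, the reported results would not show it either.

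**What to change.** 1. In Table 8-3, replace the two-point lead-in with one reference: the last organ staging on or before the first ruxolitinib dose, matching protocol 12.4.3.
2. Enrolment was complete at 45 patients by Amendment 3, so the table edit cannot change how Day 28 was scored. The working remedy is in SAP 3.5.1 and 3.5.4:
   - For every patient whose screening and Day 1 stages differ in any organ, query the investigator's response against that baseline before database lock.
   - Report the number of such patients.
   - Restore the sensitivity analysis named in protocol 12.4.1: ORR at Day 28 from the sponsor-derived response, calculated from recorded organ stages against that baseline. The investigator-reported response stays primary.

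The cost is one line in the protocol, a few sentences in the SAP, queries on the discordant patients and one extra table. Table 8-1 already marks both stagings for the clinical database, so no new data are needed. ORR may shift slightly in either direction.
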